#### **4.3.2.3 ICU Free and Alive Days and Hospitalization Free and Alive Days**

ICU free and alive days and Hospitalization free and alive days will be analyzed in a similar way as described in [section 4.3.2.2](#).

ICU days is defined as the number of days staying in ICU as collected in the eCRF ICU log.

Hospitalization days are defined as the number of days spent in a hospital as collected in the eCRF Hospitalization log. If a subject is not discharged from the ICU or hospital within the 28-day period, the number of ICU/ Hospitalization free and alive days will be zero.

### **4.3.3 Additional Analyses**

#### **4.3.3.1 All - Cause Mortality for Month 6 and 12**

All-cause mortality at month 6 (study day 177) and 12 (study day 350) will be analyzed in a similar way as that at month 3.

#### **4.3.3.2 Organ Dysfunction**

The organ dysfunctions of interest are hepatic, renal, respiratory, and shock dysfunction.

A summary table, using the FAS population, will be presented which will include the analysis time points, baseline, Study Day 3, Study Day 7, 24 hours post last dose, Study Day 14, and Day 28 as described in the analysis visit window structure in [Section 3.3](#) of this SAP and the general definition for baseline. At each indicated time point, the number of subjects having survived to the nominal time point of the analysis visit will be presented. The denominator at each time point will be the number of subjects surviving to that particular time-point within each treatment arm or overall. The numerator will be the number of subjects with a particular organ dysfunction of interest at the time-point.

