5.15 Day 28 (+3 days) or End of Study Visit

For subjects who remain hospitalized, assessments will be performed on the 28th day using the first dosing day as Day 1. Subjects who were discharged must return to the hospital for this visit so safety assessments can be performed. For subjects who were discharged from the hospital prior to Day 28, there is a visit window of +3 days and the subject must return on Day 28–31 for the completion of this visit. If a subject is unable or unwilling to return to the hospital for this visit, it may be conducted via telephone and any required assessments that cannot be done will be recorded as protocol deviations (i.e., laboratory draws). Telephone based assessments will document the date of the call, the name of the person initiating the call, the name and relationship to the subject of the person providing the information if the subject is unable to do so, and the survival status of the subject. Additionally, the subject/person providing the information will be asked about any potential adverse events, significant bleeding inclusive of any major bleeding events, or re-hospitalizations that the subject may have had since their discharge date and any changes to medications they are taking.

The End of Study Visit occurs whenever the subject discontinues study participation (as defined in **Section 2.7.2.2**) from the **study** prior to Day 28.

Perform/record the following:

- Changes in concomitant medications
- Blood product administration
- Adverse Events/Serious Adverse Events
- Assessment of ICU stay and hospitalization
- Complete the Organ Dysfunction (OD) assessments of Shock, Ventilator, Dialysis
- Interventions/Surgeries
- Major Bleeding Events

Blood will be obtained for following local laboratory tests:

- PaO₂/FiO₂ (only if vented and not collected as SOC)
- Complete Blood Count with differential (RBC, Hemoglobin, Hematocrit, and WBC with differential count)
- Platelet count
- Coagulation Panel (Prothrombin time and INR)

Additional blood samples will be drawn for analysis at the central laboratory:

- Serum Chemistry (Na, K, Cl, Bicarbonate, Glucose, Ca, BUN, Creatinine, ALT, AST, Alkaline Phosphatase and Total bilirubin)

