10.4 Handling of Missing Data

Missing data will not be imputed for summarization; summary statistics will be reported based upon observed data.

Exception: for testing of the primary endpoint, Day 28 mortality status, subjects with unknown mortality status will be imputed. Investigators will be asked to assess if at the last point they had

contact with the subject, the subject's health was such that it was unlikely they would be alive at Day 28. If so, it will be assumed the subject was dead at Day 28 otherwise they will be classified as alive for the primary analysis.

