#### **3.6.4 Organ Dysfunction and INR**

The percent of subjects with Organ Dysfunction (Hepatic, Renal, Respiratory and Shock) and subjects INR scores will be summarized with descriptive statistics at Baseline, Day 3, Day 7, 24 hours post last dose, Day 14 and Day 28. For the organ dysfunction summary, the denominator will be subjects alive on the given mortality day (24 hours post last dose will not be summarized) and the numerator will be limited to subjects in the denominator. Subjects will be counted as having an organ dysfunction at each timepoint based on the analysis visit window structure found in [Table 1](#) of this SAP (if any of the events listed below occur within these windows the subjects is classified as having the dysfunction at that visit). Additionally, shift from baseline dysfunction status to post baseline status at each timepoint will be summarized. Organ dysfunction is defined as

Hepatic Dysfunction: Central lab bilirubin greater than or equal to 2.0 mg/dL

Renal Dysfunction: Central lab creatinine greater than or equal to 2.0 mg/dL

Respiratory Dysfunction: Mechanical ventilation as indicated from the ventilation log.

Shock Dysfunction: Vasopressor used as indicated on the vasopressor CRF page.

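### In the descriptive organ-dysfunction table, survivors with no central laboratory result are in effect counted as free of hepatic and renal dysfunction

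*SAP*

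**What the plan says.** SAP 3.6.4 and 4.3.3.2 describe one table: the percentage of subjects with hepatic, renal, respiratory and shock dysfunction at baseline and at Days 3, 7, 14 and 28.

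- **Denominator.** SAP 4.3.3.2: "The denominator at each time point will be the number of subjects surviving to that particular time-point within each treatment arm or overall". SAP 3.6.4 agrees: "the denominator will be subjects alive on the given mortality day". Neither requires that a result was obtained.
- **Numerator.** SAP 4.3.3.2: "The numerator will be the number of subjects with a particular organ dysfunction of interest at the time-point". SAP 3.6.4 adds that "the numerator will be limited to subjects in the denominator".
- **Definitions.** Hepatic: "Central lab bilirubin greater than or equal to 2.0 mg/dL". Renal: "Central lab creatinine greater than or equal to 2.0 mg/dL". Respiratory dysfunction comes from the ventilation log and shock from the vasopressor CRF page.
- **Missing data.** Protocol 10.4: "Missing data will not be imputed for summarization; summary statistics will be reported based upon observed data". Its only exception is the test of Day 28 mortality. SAP 3.4 confines imputation to the same analysis. SAP 4.3.3.4 summarises creatinine and bilirubin themselves only for subjects with non-missing values.
- **Visits without blood draws.** If a subject cannot or will not return for Day 28, Protocol 5.15 says "it may be conducted via telephone and any required assessments that cannot be done will be recorded as protocol deviations".

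**The concern.** For the two laboratory-defined organs, the denominator needs only survival, while the numerator needs survival and a laboratory value. The percentage therefore combines two groups that the table does not separate: survivors shown to be below the threshold, and survivors who were not measured. No section adds a missing category to this table or says how an unmeasured survivor is to be handled.

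Two things follow. The hepatic and renal percentages fall as missingness rises, even if organ function is unchanged. And if the arms differ in the share of survivors without a result, the table can show a difference between arms that comes only from that. The same missing creatinine would be left out of the laboratory summary in SAP 4.3.3.4 and treated as below 2.0 mg/dL here.

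**Working it through.** **Step 1: can a survivor lack a result?** Yes, by several routes that the documents foresee.

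- Day 28 may be done by telephone, without draws (Protocol 5.15).
- After discharge, Protocol Appendix D requires organ-dysfunction assessments only on Days 14 and 28. A survivor discharged on Days 1–6 has no required Day 7 draw.
- Survival status is still collected after consent is withdrawn (Protocol 2.7.2.2), while study procedures stop.
- SAP Table 1 assigns Study Days 24–32 to Day 28. A subject discharged on Day 20 whose Day 28 visit is by telephone has a discharge draw outside that window and no other draw inside it.

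**Step 2: the identity.** The documents state no figure to reproduce. Let N be the survivors at a time point, m the share of them with no central result in the window, and p the dysfunction rate among those with a result.

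- Numerator = p × N × (1 − m)
- Percentage under the SAP = p × N × (1 − m) / N = p × (1 − m)
- Percentage on observed data = p
- Gap = p × m

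**Step 3: size.** Neither p nor m is in the documents. Both are assumptions, with p from 10% to 30% and m from 5% to 30%. Percentage under the SAP:

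| p | m = 5% | m = 10% | m = 20% | m = 30% |
|---|---|---|---|---|
| 10% | 9.5 | 9.0 | 8.0 | 7.0 |
| 20% | 19.0 | 18.0 | 16.0 | 14.0 |
| 30% | 28.5 | 27.0 | 24.0 | 21.0 |

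**Step 4: unequal missingness.** With the same p in both arms, the apparent difference is p × (difference in m). For a 10-point difference in m this is 1, 2 or 3 points at p = 10%, 20% or 30%, in favour of the arm with more missing results.

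**Step 5: in counts.** Use the planning mortality of 24% and 16% (Protocol 10.1) only to set the number of survivors, with 400 per arm: 400 × 0.76 = 304 on placebo and 400 × 0.84 = 336 on ART-123. Assume p of about 20%, and m of 10% on placebo and 20% on ART-123.

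- Placebo: 30 without a result, 274 with one, 55 with dysfunction. SAP rule 55/304 = 18.1%; observed data 55/274 = 20.1%.
- ART-123: 67 without a result, 269 with one, 54 with dysfunction. SAP rule 54/336 = 16.1%; observed data 54/269 = 20.1%.

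The arms are equal on observed data and differ by 2.0 points under the SAP rule.

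**The case against.** **Is this a breach of the protocol's rule against imputation?** A reader might infer so, but the text does not go that far. The SAP fills in no laboratory value and never says that missing means no dysfunction. It states a denominator, which can be read as giving the share of survivors with documented dysfunction. The effect equals counting missing as normal, but that is an inference from the two rules. What stands is that the rule is not reconciled with Protocol 10.4.

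**Does it distort the endpoint on resolution of organ dysfunction?** A reader might infer this too, and the documents do not support it. That is the secondary endpoint, measured by shock-, ventilator- and dialysis-free and alive days (SAP 3.2) from eCRF logs (SAP 4.3.3's neighbour, 4.3.2.2). Bilirubin and creatinine play no part in it. The table at issue is tertiary and has no test attached.

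**Is missingness likely to be large?** The telephone option is stated for Day 28 only. Discharged subjects are required to return for Days 14 and 28, and central chemistry is drawn at discharge and at early treatment termination. The windows are wide (Study Days 10–18 and 24–32), so a discharge draw can often fill the slot. All this lowers m but does not remove the problem. A reader could also compare the number of observations in the SAP 4.3.3.4 summaries with the survivor counts, but would still have no observed-data percentage for dysfunction.

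**Is an observed-data denominator better?** Not automatically, and this is the strongest objection. Discharged survivors without draws may be healthier. Suppose 80% of survivors have a result with 15% dysfunction, and 20% have none with 2% dysfunction (all assumed). The true rate is 0.80 × 15 + 0.20 × 2 = 12.4%. The SAP rule gives 0.80 × 15 = 12.0%, and the observed-data rule gives 15.0%. Here the SAP rule is nearer the truth. This stands, and it is why the missing counts have to be shown whichever percentage is printed.

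**Conclusion.** The point holds as a minor one about reporting. For the hepatic and renal rows, the stated rules mix unmeasured survivors with those shown to be below the threshold, and the documents neither acknowledge this nor square it with Protocol 10.4 and SAP 4.3.3.4.

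The understatement relative to the observed-data percentage is p × m, and unequal missingness alone can produce a difference of 1–3 points under the assumptions above. Those sizes depend on assumed p and m and on equal p in the two arms; the documents cannot confirm them. They do not establish how far the table lies from the true prevalence, or in which direction the observed-data percentage would err. The primary analysis, its alpha and power, the secondary endpoints, and the log-based respiratory and shock rows are unaffected.

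**What to change.** In SAP 3.6.4 and 4.3.3.2, for hepatic and renal dysfunction only:

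1. Report the percentage among survivors with a non-missing central bilirubin or creatinine in the analysis window.
2. Show, for each arm and time point, the number of survivors with no result.
3. If the all-survivor percentage is kept, print it beside the first and label it as counting missing results as no dysfunction.

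Leave the respiratory and shock rows as they are. The same edit can settle whether 24 hours after the last dose is a time point for this table: SAP 3.6.4 says it will not be summarised for organ dysfunction, while 4.3.3.2 lists it.

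The cost is a sentence or two in the SAP and a few extra table rows, with no new data. The downside is a smaller denominator that may over-represent subjects still in hospital; the missing counts let the reader judge that.

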### **2.3 Sample Size**

The primary analysis for this study will be based on a stratified Cochran-Mantel-Haenszel test. For sample size and power calculations a Chi-squared test has been used. A sample size of 800 subjects provides approximately 80% power if the following assumptions are made:

1. 5% two-sided alpha level
2. 8% treatment effect (24% placebo mortality rate vs. 16% ART-123 mortality rate).
3. 1 to 1 randomization

The assumed treatment effect and mortality rates are based upon post-hoc results from study 2-001 and assume the day 28 mortality status will be known for all subjects.

A sample size of 800 subjects and these assumptions also provides 32% power for a 0.1% two-sided  $\alpha$  level. If the true treatment effect is 12% (24% vs. 12%), a sample size of 800 provides greater than 80% power when a 0.1% alpha level is used.

In this 800 subject study, an observed treatment benefit of approximately 6% is expected to result in a p-value less than 5% and a difference of approximately 9% is expected to result in a p-value less than 0.1%.

The sample size and power calculations were performed with Pass 2007.

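### The tertiary organ-dysfunction percentages are reported among survivors only, so the arms are set side by side on denominators that treatment can change, and the two SAP sections defining them disagree

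*SAP*

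**What the plan says.** Organ dysfunction (hepatic, renal, respiratory, shock) at Baseline and Days 3, 7, 14 and 28 is a tertiary efficacy endpoint (SAP 3.2; Protocol section 6). Two SAP sections describe its summary.

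- SAP 4.3.3.2, under additional analyses, states: "The denominator at each time point will be the number of subjects surviving to that particular time-point within each treatment arm or overall". It also presents the number who survived to the nominal time of each visit. It does not limit the numerator to those survivors, and it lists 24 hours post last dose among the time points.
- SAP 3.6.4 states: "the denominator will be subjects alive on the given mortality day (24 hours post last dose will not be summarized"). It limits the numerator to subjects in the denominator. The same paragraph then adds shifts from baseline dysfunction status, with no denominator of their own and no category for death.

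Both sections are descriptive and plan no test. SAP 4.1 sets the default denominator to all subjects in the group within the analysis population, unless otherwise specified.

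The secondary measures of organ-dysfunction resolution are shock, ventilator and dialysis free and alive days (SAP 3.2). They are computed as alive days minus event days and tested with a van Elteren test (SAP 3.6.3 and 4.3.2.2).

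**The concern.** Death is the primary endpoint and also decides who enters these tables. If ART-123 lowers mortality, its Day 28 table contains patients whose counterparts on placebo have died and are not counted. Should those patients carry more organ dysfunction than other survivors, the ART-123 percentage rises even though the drug has harmed no organ. Neither section plans an all-subject version or cautions the reader. SAP 4.3.1.1 does give a caution of that kind for subgroups formed on post-baseline factors.

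This matters most for hepatic dysfunction (bilirubin) and renal dysfunction defined by creatinine. Shock, ventilation and dialysis each have a free-and-alive-days endpoint in which an early death costs days. Bilirubin and creatinine have none, so the survivor-only percentage and the shift are their only planned dysfunction-rate summaries.

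**Working it through.** **Inputs from SAP 2.3.** "A sample size of 800 subjects provides approximately 80% power if the following assumptions are made": "5% two-sided alpha level"; "8% treatment effect (24% placebo mortality rate vs. 16% ART-123 mortality rate"); "1 to 1 randomization". This gives 400 per arm.

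**The plan's own figure.** Pooled rate 0.20. Null SE = √(2 × 0.20 × 0.80 / 400) = 0.02828. Alternative SE = √(0.24 × 0.76 / 400 + 0.16 × 0.84 / 400) = 0.02814. Power = Φ[(0.08 − 1.96 × 0.02828) / 0.02814] = 80.9%, which matches. At two-sided 0.001 the same formula gives 32.1%, against the stated 32%. The mortality rates can therefore be used as they stand.

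**Denominators at Day 28.** Placebo 400 × 0.76 = 304; ART-123 400 × 0.84 = 336. The 32 extra survivors are 32/336 = 9.5% of the ART-123 denominator.

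**Survivor-only percentage.** Let p be the dysfunction rate in patients who would survive on either arm and q the rate in the 32 extra survivors. Neither is in the documents. Assume also that the drug has no direct effect on organs and causes no deaths.

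- Placebo shows p; ART-123 shows (304p + 32q)/336.
- Gap = (32/336)(q − p).

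With p = 15% and q = 40%: (45.6 + 12.8)/336 = 17.4% against 15.0%, a gap of 2.4 points. SE = √(0.15 × 0.85/304 + 0.174 × 0.826/336) = 0.029, so the gap is about 0.8 SE.

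Gap in points over a range of assumptions:

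| p | q = 30% | q = 40% | q = 50% |
|---|---|---|---|
| 10% | 1.9 | 2.9 | 3.8 |
| 15% | 1.4 | 2.4 | 3.3 |
| 20% | 1.0 | 1.9 | 2.9 |

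These run from 0.3 to 1.5 SE, and seven of the nine cells reach half an SE. When q = p the gap is zero. The gap is cancelled if the drug cuts dysfunction in the other survivors by a relative (32/304)(q − p)/p, which is 17.5% at p = 15%, q = 40%.

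**Same example on all 400 per arm.**

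| | Placebo | ART-123 |
|---|---|---|
| Dead | 96 (24.0%) | 64 (16.0%) |
| Alive with dysfunction | 45.6 (11.4%) | 58.4 (14.6%) |
| Alive without dysfunction | 258.4 (64.6%) | 277.6 (69.4%) |

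Alive without dysfunction favours ART-123 by 4.8 points, which equals 8 × (1 − 0.40). All of it comes from survival, because the example gives the drug no organ effect.

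**The two sections compared.**

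- *Survival definition.* SAP 3.6.4 uses the mortality day; 4.3.3.2 uses the nominal time. SAP Table 1 puts Day 3 at 48 hours and Day 7 at 144 hours. Mortality day is defined only for Day 28 (SAP 3.6.1). Extended to Days 3 and 7 it would fall at 72 and 168 hours, 24 hours later. At Days 14 and 28 the two agree.
- *Numerator.* The Day 14 window covers Study Days 10 to 18. Under 4.3.3.2 as written, a subject ventilated on Day 10 who dies on Day 12 could be in the numerator but not the denominator. SAP 3.6.4 prevents this.
- *24 hours post last dose.* Excluded in 3.6.4, listed in 4.3.3.2.
- *Missing assessments.* Protocol 5.15 allows a telephone Day 28 visit without laboratory draws. Such a survivor stays in the denominator and in effect counts as free of hepatic and renal dysfunction.

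**The case against.** The strongest reply is that little rides on these tables. They are tertiary, untested and filed under additional analyses, and no decision rule uses them. The organ-dysfunction measures that support the secondary objective are the tested free-and-alive-days endpoints, which already penalise death. Much of the all-subject picture can be recovered: 4.3.3.2 prints the survivor counts, SAP 4.1 requires counts beside percentages, and SAP 4.3.1.1 tabulates dead, alive and unknown by arm. All of this stands and limits the point to a reporting improvement. It does not cover bilirubin and creatinine, missing assessments or the shift table.

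The illustration also has its direction built in: every cell sets q above p and gives the drug no organ benefit. That stands too. The documents give no support for the extra survivors being sicker, so the result is a possibility. Only Day 28 can be computed; earlier days depend on the timing of deaths, which is not given.

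A reader might infer that the shift table drops the dead from its denominator. The SAP does not say so: 3.6.4 states no denominator for shifts, and the 4.1 default of all subjects may apply. A reader might also infer that alive without dysfunction should become the sole basis for comparing the arms. The documents give no ground for that, and the 4.8-point example shows that this composite can simply restate mortality.

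**Conclusion.** The point holds as a modest reporting defect. The survivor-only denominators (304 vs 336 at Day 28 on planned mortality) depend on the primary outcome, so an arm difference in these percentages cannot be read as a drug effect on organs. Under the assumed p of 10% to 20% and q of 30% to 50%, with no direct organ effect and no deaths caused by the drug, the distortion is 1.0 to 3.8 points against ART-123. It vanishes if the extra survivors resemble the others, and a direct organ benefit can offset it.

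A reader might go further and conclude that ART-123 will look worse, or that the plan's organ-dysfunction efficacy assessment as a whole is biased. The documents support neither. The first depends on rates they do not give. The second overlooks that the mortality test and the free-and-alive-days endpoints are unaffected.

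The conflicts between 3.6.4 and 4.3.3.2 on the numerator and on 24 hours post last dose stand on the text alone. The 24-hour difference in survival definition at Days 3 and 7 rests on extending a term defined only for Day 28.

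**What to change.** In SAP 3.6.4 and 4.3.3.2:

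1. Keep the survivor-only percentages. Beside them, at each time point, give dead, alive with dysfunction, alive without dysfunction, and alive with assessment missing, as percentages of all Full Analysis Set subjects. Show unknown vital status separately where it occurs, so that the rows add up.
2. Add a dead category to the baseline shift table and state its denominator.
3. Present both views, and say that arm differences in the survivor-only percentages are not to be read as a drug effect on organs.
4. Use one survival definition in both sections, based on date of death relative to first dose. Carry 3.6.4's numerator restriction into 4.3.3.2. Decide whether 24 hours post last dose is summarized.

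The cost is a few extra rows in one table and a category in another, with no new data. The drawback is that the all-subject breakdown partly restates mortality, which is why it belongs beside the survivor percentages and should not replace them.
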